1.4.2. Clinical Studies

PTC857 was evaluated in Study PTC857-CNS-001-PD, a 3-part, Phase 1, single-center, double-blind, randomized, placebo-controlled, single- and multiple-ascending-dose, as well as food effect study of PTC857 in healthy volunteers. There were no treatment-emergent serious adverse events (TESAEs), no treatment-emergent adverse events (TEAEs) leading to discontinuation of PTC857, and no TEAEs leading to death.

PTC857 was also evaluated in 6 additional completed Phase 1 studies:

- Study PTC857-CNS-002-HV was a Phase 1, 2-period, crossover, relative bioavailability study of 2 formulations in healthy volunteers.
- Study PTC857-CNS-003-HV was a Phase 1, randomized, open-label, 3-period, 6-sequence crossover study to investigate the effect of food on the PK and safety of PTC857 in healthy volunteers.
- Study PTC857-DDI-101-HV was a Phase 1, open-label, fixed-sequence, 3-part study to investigate the effect of multiple doses of PTC857 on the PK of caffeine (a cytochrome P450 [CYP] 1A2 substrate), midazolam (a CYP3A4 substrate), and bupropion (a CYP2B6 substrate).
- Study PTC857-JPB-102-HV was a Phase 1, open-label, single-dose study to evaluate the PK, safety, and tolerability of PTC857 in healthy Japanese and Caucasian adult subjects.
- Study PTC857-CNS-004-HV was a Phase 1, open-label, multiple-dose, absorption, metabolism, and excretion study in healthy male participants to assess the metabolism, rates and routes of excretion, mass balance, and PK of ¹⁴C-PTC857.
- Study PTC857-PAL-104-HV was a Phase 1, single-part, randomized, single-blind study designed to evaluate the taste profile of PTC857 Oral Solution.

There were no TESAEs, no TEAEs leading to discontinuation of PTC857, and no TEAEs leading to death in these studies, with the exception of 1 TEAE of acne that led to discontinuation of a subject in Study PTC857-CNS-003-HV.

Exposure to PTC857 in completed clinical studies included 191 subjects (healthy volunteers) at doses ranging from 100 to 1000 mg. The longest treatment duration was 14 days. The clinical safety data suggest that PTC857 is safe and well tolerated. No TESAEs were reported.

Based on the results of Study PTC857-CNS-003-HV, the PK parameters of PTC857 were higher under low- and high-fat conditions when compared with fasted conditions, but were comparable between the 2 fed states; hence, PTC857 should be taken with food.

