1.5.3. Summary of Safety Risks

There are no important identified or important potential risks for PTC857.

The following potential risks have been recognized to date for PTC857:

• Lipoprotein changes

For further details on each risk, risk mitigation strategies, as well as adverse drug reactions recognized to date, and other important safety topics for PTC857, see the IB.

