4.3. Exclusion Criteria

Individuals are not eligible to participate in this study if they have met or meet any of the following exclusion criteria at either the Screening Visit or the Baseline Visit, unless otherwise stated:

- 1. History of allergies or adverse reactions to any of the excipients in the study drug formulation
- 2. Females who are pregnant or nursing or plan to become pregnant during the study
- 3. Subjects with clinically significant gastrointestinal, renal, hepatic, neurologic, hematologic, endocrine, oncologic, pulmonary, immunologic, psychiatric, or CV/ischemic disease or any other condition that, in the opinion of the investigator, would jeopardize the safety of the subject or impact the validity of the study results
- 4. Any clinically significant medical or psychiatric condition or medical history that, in the opinion of the investigator or the medical monitor, would interfere with the subject's ability to participate in the study or increase the risk of participation for that subject
 - Note: The lumbar puncture may be skipped for an individual subject if the investigator deems it appropriate, and after discussion with the medical monitor. Subjects with a contraindication to lumbar punctures, such as but not limited to space-occupying lesion with mass effect, increase of intracranial pressure due to increased CSF pressure, posterior fossa mass, Arnold-Chiari malformation, anticoagulation medication use, coagulopathy, uncorrected bleeding diathesis, congenital spine abnormality, previous adverse event associated with a lumbar puncture or skin infection at the puncture site, should not undergo the lumbar punctures as listed in the Schedule of Events. These subjects may still enroll in the study and should undergo all other study procedures.
- 5. Hepatic insufficiency, defined as liver function tests (LFTs) (ie, AST and/or ALT) ≥3× the upper limit of normal (ULN), or bilirubin ≥1.5× the ULN (except in the case of Gilbert's disease)

- 6. Moderate or worse renal insufficiency, defined as an estimated glomerular filtration rate (eGFR) of <60 mL/min
- 7. Current participation in any other investigational study with an investigational product or participation within 30 days prior to the start of the Screening Period or 5 half-lives of the previously taken investigational drug, whichever is longer

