7.2.5. Clinical Laboratory Assessments

Blood samples will be taken under fasted conditions. Subjects will not be allowed to eat for a period of 8 hours prior to blood sampling or drink (except water) for a period of 4 hours prior to blood sampling.

All clinical laboratory tests listed in Table 5 will be performed as outlined in the Schedule of Assessments (Table 1 and Table 2). In addition, laboratory safety tests may be performed at various unscheduled timepoints if deemed necessary by the PI or designee.

Clinically significant laboratory abnormalities must be reported by the investigator as an AE or SAE as appropriate.

The results of all laboratory tests will be provided to the investigator in order for the investigation to make an assessment of clinical significance, with the exception of the lipid (cholesterol [total], low-density lipoprotein [LDL], high-density lipoprotein [HDL], triglycerides, apolipoprotein A, apolipoprotein B), amylase, and lipase values. The lipid, amylase, and lipase values (both individual subjects and study level) will be monitored regularly for the entirety of the study by the DSMB.

Table 5: Summary of Clinical Laboratory Tests

| Hematology | Chemistry | Urinalysis | Others |
|-------------------------|------------------------------------|------------------|----------------------|
| Hemoglobin | Urea | Urobilinogen | Serum/urine |
| Hematocrit | Creatinine | Nitrite | pregnancy test |
| RBC count | Fasting glucose | pН | (β-HCG) ^b |
| Reticulocytes | Sodium | Glucose | FSH |
| Platelet count | Potassium | Total protein | Coagulation (PT |
| WBC count | ALT | Erythrocytes | [sec], PT [INR], |
| Neutrophils | AST | Leukocytes | aPTT) |
| Eosinophils | GGT | Ketones | |
| Monocytes | Bilirubin (total, direct/indirect) | Microscopya | |
| Basophils | Alkaline phosphatase | Specific gravity | |
| Lymphocytes | Albumin | Bilirubin | |
| Mean corpuscular volume | Cholesterol (total) | | |
| | LDL | | |
| | HDL | | |
| | Triglycerides | | |
| | LDH | | |
| | Amylase | | |
| | Lipase | | |
| | Apolipoprotein A | | |
| | Apolipoprotein B | | |

Abbreviations: β-HCG, beta human chorionic gonadotropin; ALT, alanine aminotransferase; aPTT, activated partial thromboplastin time; AST, aspartate aminotransferase; FSH, follicle-stimulating hormone:

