7.3.5.1. Assessments of Severity of Adverse Events

The severity of AEs will be graded using the Common Terminology Criteria for Adverse Events (CTCAE) Version 5.0. For each episode, the highest severity grade attained should be reported.

The investigator will make an assessment of severity for each AE and SAE reported during the study and assign it to 1 of the following categories (Table 7).

Table 7: Grading of Adverse Events

| Grade | Adjective | Description |
|-------|------------------|--|
| 1 | Mild | Asymptomatic or mild symptoms; clinical or diagnostic observations only; intervention not indicated. |
| 2 | Moderate | Minimal, local, or noninvasive intervention indicated, limiting age appropriate instrumental Activities of Daily Living (ADL). Instrumental ADL refers to preparing meals, shopping for groceries or clothes, using the telephone, managing money, etc. |
| 3 | Severe | Severe or medically significant but not immediately life-threatening; hospitalization or prolongation of hospitalization indicated; disabling, limiting self-care ADL. Self-care ADL refers to bathing, dressing, and undressing, feeding self, using the toilet, taking medications, and not bedridden. |
| 4 | Life-threatening | Sign or symptom results in urgent intervention. |
| 5 | Fatal | Sign or symptom results in death. |

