Laboratory data will be summarized descriptively by visit for each laboratory parameter by treatment group and overall. Both observed results and changes from baseline will be summarized for continuous variables. Laboratory values will be categorized as clinical grade (low/normal/high) according to normal ranges. Shifts from baseline to the last on-treatment grade and the worst on-treatment grade will be presented. For these shift summaries, for the last on-treatment summary only scheduled visits will be taken; for the worst on-treatment summaries unscheduled assessments will be included in the assessment of worst. Both worst low and worst high will be summarized.

Laboratory values that are below the limit of quantification will be imputed as the lower-limit of quantification, similarly, values above the limit of quantification will be imputed as the upper-limit of quantification for the summary statistics. But for listings, the values will be presented as recorded.

By-subject listings of all the laboratory parameters will be presented that clearly indicate out of normal range values and possible abnormal values for the safety analysis set.

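### Laboratory shift tables use only low/normal/high, so the number of subjects per arm with marked liver-enzyme, lipid, amylase or lipase elevations is not tabulated

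*SAP*

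**What the plan says.** SAP (Part A) Section 6.3 sets the rule: "Laboratory values will be categorized as clinical grade (low/normal/high) according to normal ranges". It then says "Shifts from baseline to the last on-treatment grade and the worst on-treatment grade will be presented". Unscheduled values count towards the worst value but not the last. SAP (Parts B/C) Section 6.4 repeats the three-level rule and the two shift tables.

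Other routes for laboratory data in the plan are:

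- By-visit summaries by arm: "Both observed results and changes from baseline will be summarized for continuous variables". SAP (Part A) Section 3.1 gives the statistics as n, mean, SD, median, minimum and maximum.
- Section 3.2.4 leaves unscheduled values and retests out of by-visit summaries but lets them feed tables of significant abnormalities where applicable. No laboratory criterion for those tables appears.
- By-subject listings show every value and flag those out of range.
- Protocol Section 7.2.5 requires clinically significant laboratory abnormalities to be reported as AEs or SAEs. Protocol Section 7.3.5.1 adds: "The severity of AEs will be graded using the Common Terminology Criteria for Adverse Events (CTCAE) Version 5.0". SAP (Part A) Section 6.2 tabulates Grade 3 or higher TEAEs.

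Investigators receive laboratory results to "make an assessment of clinical significance, with the exception of the lipid (cholesterol [total], low-density lipoprotein [LDL", and the exception goes on through the rest of the lipid panel to amylase and lipase. The DSMB monitors those values instead.

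**The concern.** A shift table should show how many subjects in each arm moved to a worrying level. Here the top level runs from just above the ULN to any multiple of it. Protocol Section 4.3 excludes only "AST and/or ALT) ≥3× the upper limit of normal (ULN), or bilirubin ≥1.5× the ULN", so subjects can enter with raised values. A large further rise in such a subject then reads as no shift, and a large rise from a normal baseline reads the same as a trivial one.

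A small tail of marked hepatic or lipid responders is what a first trial of this length should be able to count by arm. Of the completed clinical studies, Protocol Section 1.4.2 says "The longest treatment duration was 14 days". This trial doses for 24 weeks under randomisation and up to 160 weeks in total. The one potential risk listed in Protocol Section 1.5.3 is "Lipoprotein changes", and Section 1.5.1 reports reversible lipid changes in healthy volunteers.

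**Working it through.** The plan states no figure to reproduce. The check applies the three-level rule to illustrative values, then asks what the other planned tables would show.

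**Step 1. The shift rule.** Values are in multiples of ULN; above 1 is high.

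| Baseline | Worst | Change | Cell |
|---|---|---|---|
| 2.9 | 3.0 | 0.1 | high to high |
| 2.9 | 20 | 17.1 | high to high |
| 1.1 | 1.2 | 0.1 | high to high |
| 1.1 | 10 | 8.9 | high to high |
| 0.8 | 1.05 | 0.25 | normal to high |
| 0.8 | 10 | 9.2 | normal to high |

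Magnitude is lost from normal and high baselines alike, so the point does not depend on how many subjects start above the ULN. The documents do not give that share.

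**Step 2. The denominator.** Laboratory analyses use the Safety Set, which is drawn from ITT2, not the ITT1 arm of 205. With about 340 randomised 2:1 and all dosed (assumption), PTC857 has 340 × 2/3 = 226.7, about 227.

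**Step 3. By-visit summaries, ALT example.** Assume 3 of 227 go from 1.5 to 10 × ULN at one scheduled visit and the rest do not change. Then p = 3/227 = 0.0132.

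- Mean change = 3 × 8.5/227 = 0.11 ULN; median change = 0.
- SD of change = 8.5 × √(p(1 − p)) = 8.5 × 0.114 = 0.97 ULN.
- Maximum change = 8.5 ULN; maximum value at least 10 × ULN.
- Shift table: all three sit in high to high, beside any subject who stayed at 1.5 × ULN.

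The SD and maximum respond to the tail; the mean and median hardly do. But the maximum is the same for one subject or three.

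**Step 4. By-visit summaries, triglyceride example.** If 10 of 227 baseline-high subjects triple (+200%) and the rest do not change, the mean change is 10/227 × 200% = 8.8%, the median is 0, and the SD is 200 × √(0.0441 × 0.9559) = 41 percentage points. Percent change is used here for illustration only.

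**Step 5. Limits of the by-visit route.** Unscheduled values are left out. For a retest under the same visit number the last value is used, so a spike followed by a lower retest drops out. Values above the quantification limit are set to that limit.

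**Step 6. Limits of the AE route.** Protocol Section 7.3.1 says abnormalities that need neither intervention nor further investigation should not be reported as AEs, so the counts rest on investigator judgement. For lipids, amylase and lipase the investigator does not see the result.

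**Step 7. Parameter lists.** Protocol Table 5 includes amylase, lipase and apolipoproteins A and B. None of the four appears in the parameter groups of SAP (Part A) Section 6.3 or SAP (Parts B/C) Section 6.4, on which the laboratory tables are built.

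**Step 8. Comparison within the SAP.** Section 6.5 counts QT and QTcF above 450, 480 and 500 ms and changes above 30 and 60 ms. Section 6.8 bands percent weight change. Section 6.2.3 counts ALSFRS-R declines of 18 points or more. Laboratory values have no such bands.

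**The case against.** A reader might infer that the planned output cannot reveal severe elevations at all, or that the shift is the only subject-level laboratory analysis. The documents support neither reading. By-visit tables carry the maximum and SD by arm, and in the ALT example both signal the tail. Listings give every value. Investigators do receive ALT, AST and bilirubin, so a marked hepatic rise can be reported, graded by CTCAE and appear in the Grade 3 or higher TEAE table by treatment. The hepatic part of the point is therefore the weaker part.

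Three further objections deserve weight:

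- The table shells are a separate document that is not available here, so a graded table in them cannot be ruled out. The criteria still belong in the SAP, as those for QT and weight do.
- Protocol Section 1.5.3 states that there are no important identified or important potential risks, and the DSMB monitors lipids, amylase and lipase at subject and study level. That is oversight; it does not put a by-arm count in the report.
- The exact reporting bands are a matter of choice, and safety analyses are descriptive with no formal comparison. The improvement is real but modest.

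It would also be wrong to infer that a 160-week randomised comparison is lost. Randomised treatment lasts 24 weeks; later dosing is open-label.

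**Conclusion.** The point holds in limited form. The shift tables in both SAPs do not grade magnitude from any baseline level, and no laboratory table with defined criteria counts subjects by arm with marked liver-enzyme, lipid, amylase or lipase elevations. The other routes can show that an extreme exists but do not supply that count from laboratory values.

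The gap matters most for lipids, amylase and lipase. Their results are withheld from investigators, lipoprotein change is the only listed potential risk, and amylase, lipase and the two apolipoproteins are missing from the SAP parameter groups.

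The size figures are illustrations. They assume about 227 dosed PTC857 subjects, the stated numbers of responders, and no change in everyone else. No hypothesis test, alpha or power is affected.

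**What to change.** In SAP (Part A) Section 6.3 on the Safety Set, and in SAP (Parts B/C) Section 6.4 on the LTE Safety Set, add by-arm counts of the worst post-baseline value, unscheduled values included:

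- By CTCAE v5.0 grade, against baseline grade, for analytes that have one. The protocol already uses this scale for AEs.
- By multiple of ULN for ALT, AST and bilirubin, for example above 3, 5 and 10 times for ALT and AST and above 1.5 and 2 times for bilirubin. Add a combined category such as ALT or AST above 3 times with bilirubin above 2 times. These are reporting bands only.
- By category of percent change from baseline for lipids without a grade.

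Add amylase, lipase and apolipoproteins A and B to the parameter groups. State that these are the criteria for the significant-abnormality tables, so that the reference to them is no longer undefined. Keep the low/normal/high shifts for the other analytes.

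The cost is some table programming and a few more descriptive safety tables. No new data are needed.

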6.4. Vital Signs

Vital signs including systolic and diastolic blood pressure (mmHg), pulse rate (beats/min), body temperature (°C), Oxygen saturation (SpO₂), and respiratory rate (breaths/min) will be evaluated

at Screening, Day 1, Day 29, Day 57, Day 85, Day 113, Day 141, and Day 169, as well as the ET visit where applicable.

For convenience, the conversion for temperature: Temperature (in $^{\circ}$ C) = (Temperature [in $^{\circ}$ F]-32) x (5/9).

Absolute results and changes from baseline will be summarized descriptively by visit for each parameter, by treatment group and overall.

6.5. 12-Lead Electrocardiogram

The following 12-lead ECG will be performed at Screening, Day 1, Day 85, and Day 169, as well as the ET visit where applicable.

- Heart rate (bpm)
- QRS Interval (msec)
- PR Interval (msec)
- QT interval (msec)
- QTcF Interval (msec)
- Overall Interpretation

Descriptive summaries will be presented for the ECG parameter values and change from baseline by visit for all quantitative measurements. Overall interpretation of ECG assessment will be summarized by counts and percentages. QT and QTcF will be categorized as follows, and the category based on actual value will be summarized by treatment group at each visit as well as the category at each post-baseline visit based on change from baseline per the following criteria:

Type of Value	Category 1	Category 2	Category 3
Actual value	> 450 ms	> 480 ms	>500 ms
Change from Baseline	> 30 ms	>60 ms	

A by-subject listing of all ECG parameters will be provided.

6.6. Physical Examination

A detailed physical examination will be performed at Screening visit and targeted physical examination will be performed at Day 1, Day 85, and Day 169 as well as the ET visit where applicable.

For the remaining visits, a symptom-driven physical examination will be performed as per the investigators' discretion. Physical examination including details of clinically significant findings, will be listed.

6.7. Columbia-Suicide Severity Rating Scale

The C-SSRS is a questionnaire that prospectively assesses suicidal ideation and suicidal behavior (Posner 2011). The C-SSRS, which uses a semi-structured interview to probe subject responses, is administered by an individual who has received training and certification in its administration. During the Screening Visit (Day -56), the "baseline" version of the C-SSRS is administered. This

version assesses suicidal ideation and suicidal behavior during the subject's lifetime. At all subsequent visits, the "since last visit" version is administered.

Counts and percentage of subjects who experience suicidal ideation, suicidal behavior or neither (no ideation or behavior) will be summarized by treatment group at baseline and double-blind treatment period.

The C-SSR instrument consists of 11 Yes/No questions as shown in the table below and is grouped by type question, i.e., suicidal ideation questions and suicidal behavior questions. Within each type/group the questions are re-ordered by increasing severity. In addition, subjects are assessed for any self-injurious behavior without suicidal intent.

C-SSRS Item	Derivation
Suicidal ideation	 A "yes" answer to any one of the following five questions. Wish to be dead. Non-specific active suicidal thoughts. Active suicidal ideation with any methods (not plan) without intent to act. Active suicidal ideation with some intent to act, without specific plan. Active suicidal ideation with specific plan and intent.
Suicidal behavior	A "yes" answer to any one of the following five questions. Preparatory acts or behavior Aborted attempt Interrupted attempt Actual attempt Suicidal behavior Completed suicide
Self-injurious behavior without suicidal intent	A "yes" answer to the following question from suicidal behavior section on the C-SSRS: Has subject engaged in Non-Suicidal Self-Injurious behavior?
Suicidal Ideation Score	Is defined as the maximum suicidal ideation category (1-5 on the C-SSRS) present at the assessment. A score of 0 is assigned if no ideation is present.

For the overall assessment of suicidal ideation and behavior during the double-blind treatment period a subject's worst finding during that period will be used.

The following tables will be generated at the end of the Double-Blind Treatment Period:

- Counts and Percentage of Subjects with Suicidal Ideation, Suicidal Behavior, and Self-Injurious Behavior without Suicidal Intent Based on the C-SSRS by Treatment group at baseline.
- Counts and Percentage of Subjects with Suicidal Ideation, Suicidal Behavior, and Self-Injurious Behavior without Suicidal Intent Based on the C-SSRS by Treatment group during the double-blind treatment period.

- Counts and Percentage of Subjects with Suicide-Related Treatment Emergent Events Based on C-SSRS by Treatment group during the Double-Blind Treatment Period.
- Shift table of changes in C-SSRS categories (ideation, behavior, or neither) from baseline to through Week 24.
- Shift table in Changes in C-SSRS Suicidal Ideation scores from baseline to through Week 24 by Treatment.

All C-SSRS assessments will be listed.

